A participant will be considered as showing clinical diarrheal illness if diarrhea is observed with at least two diarrheal bowel events within 24 hours on at least two days during the observation period beginning after the ABO809 administration (Day 1) and ending on Day 28 (see Section 8.3.2)

Resolution of diarrheal illness from Cryptosporidium infection requires ≥ 2 consecutive days with no diarrheal stools (stool sample grades 1 or 2).

Participants will be monitored daily for infection (parasitological evaluation) and diarrheal illness (clinical evaluation) during the domicile period. The monitoring of symptoms will continue in the outpatient setting with the collection of information via the CHIM diary and Safety Follow-Up Calls. Participants will provide a health and stool update daily from Day 1 through 28 in the CHIM diary. Safety Follow-Up Calls will occur on Days 35, 42, 49, and 56.

The primary endpoint is *Cryptosporidium* infection as indicated by detection of oocysts in fecal samples by EIA CCI ≥72 hours following an oral administration of ABO809 (or sooner if associated with symptoms suggestive of diarrheal illness). Secondary endpoints include characterization of diarrheal illness, safety and tolerability.

Figure 3-1 Study Design

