10.1.1.1 Adverse events of special interest

All participants may report adverse events associated with *Cryptosporidium* infection as detailed in Section 4.5 Risks and benefits. The Investigator will report AESI and follow-up accordingly; these include:

- **Gastroenteritis in the absence of** *Cryptosporidium* **infection**: In the event of gastroenteritis in the absence of *Cryptosporidium* infection, the event will be considered an AESI. The Investigator will investigate other potential causes of diarrhea, including infectious diarrhea and manage participant's care according to local standards.
- Extraintestinal cryptosporidiosis: *Cryptosporidium* infection involving the biliary tract, lungs, liver, pancreas, or other organs will be considered AESI (also see Section 4.5 Risks and benefits).
- **Persistent or recurrent cryptosporidiosis:** Persistent clinical symptoms after administration of standard of care, or after initial resolution of *Cryptosporidium* oocysts in the stool and/or diarrheal symptoms, will be considered an AESI.
- **Persistent** *Cryptosporidium* **shedding:** Persistent detection of *Cryptosporidium* oocysts in stools after treatment with nitazoxanide will be considered an AESI. Participants with persistent shedding may be treated with combination therapy as detailed in Section 6.2.3.
- **Dehydration:** Moderate or severe dehydration, as defined below will be considered an AESI.
 - Mild: dry mucous membranes; diminished skin turgor; increased oral fluids are indicated
 - Moderate: IV fluids are indicated
 - Severe: hospitalization is indicated or it is considered to have life-threatening consequences; or an urgent intervention is indicated
- **Non-intestinal sequelae:** Development of new onset non-intestinal symptoms, including eye pain or joint pain, will be considered AESI.

If any AESIs are experienced after EOS (i.e. Post-Study Safety Follow-up calls at 6 and 12 months) in which the Investigator considers there is a reasonable possibility that ABO809 caused the event, the event will be recorded and reported following the same procedure as SAEs as described in Section 10.1.3. These AESIs will be captured in the Novartis safety database, included in an addendum to the CSR and reported to the competent authorities and relevant ethics committees as per national regulatory requirements in participating countries.

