2.1.1.1 Definition of clinical and parasitological response

Diarrhea: A participant will be considered as having diarrhea if they have at least one stool sample grading 3-5 on the Stool Grading System (Table 5-5). Grade 1-2 stools are considered normal and are formed or soft stool which do not easily take the shape of the container. Grade 3-5 stools are considered diarrheal and are thick liquid, opaque watery, rice water or clear watery stool which do take the shape of the container.

Number of days to diarrhea onset: is defined as the first diarrhea stool date minus the dosing date.

Number of days of diarrhea: is defined as all days with at least one stool sample grading 3-5.

Number of days to resolution of diarrhea: is defined as the last diarrhea stool date minus the dosing date +3

Duration of diarrhea (hours): is defined as the last diarrhea stool date/time minus the first diarrhea stool date/time.

Clinical diarrheal illness: A participant will be considered as having clinical diarrheal illness if diarrhea is observed with at least two diarrheal bowel events within 24 hours on at least two days during the observation period beginning after ABO809 administration (Day 1) and ending on Day 28.

Resolution of clinical diarrhea illness: A participant will be considered recovered from diarrheal illness when no diarrhea occurred on ≥ 2 consecutive days following the last diarrhea in participants with clinical diarrhea illness.

Number of days to clinical diarrhea onset: is defined as the first day of clinical diarrhea illness date minus the dosing date.

Number of days of clinical diarrhea illness: is defined as all days of diarrhea in participants with clinical diarrhea illness. It will be set to 0 for participants with no clinical diarrhea illness.

Confidential

Number of days to resolution of clinical diarrhea illness: is defined as 48 hours after the last day of clinical diarrhea illness, i.e., last diarrhea date minus the dosing date +3 in participants with clinical diarrhea illness.

Duration of clinical diarrheal illness (hours): is defined as the last diarrhea date/time minus the first diarrhea date/time in participants with clinical diarrhea illness.

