3.2 Secondary endpoint(s)

Commercially Confidential Information

The calculation is based

on the 1-sided 80% exact confidence interval.

4 Change to protocol specified analyses

None

5 Appendix

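### SAP 2.1.1.1 gives diarrheal illness no episode boundary, so one isolated loose stool before rescue can lengthen duration and postpone resolution

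*SAP*

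**What the plan says.** **SAP 2.1.1.1.** A participant has diarrhea "if they have at least one stool sample grading 3-5 on the Stool Grading System". Clinical diarrheal illness is stricter: at least two diarrheal events within 24 hours, on at least two days up to Day 28. The derived variables are:

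- Duration of illness "is defined as the last diarrhea date/time minus the first diarrhea date/time in participants with clinical diarrhea illness".
- Recovery requires at least "2 consecutive days following the last diarrhea in participants with clinical diarrhea illness".
- Days to resolution is described as 48 hours after the last day of clinical illness, and then written as "last diarrhea date minus the dosing date +3 in participants with clinical diarrhea illness".
- Days to onset of illness runs from dosing to the first day of clinical illness.

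**Protocol Sections 3 and 8.3.2.** Resolution takes at least "2 consecutive days with no diarrheal stools (stool sample grades 1 or 2"). Neither section ties this to the last stool. Footnote 5 to Table 8-1 provides for testing the first loose stool when diarrhea relapses after clinical clearance. Section 10.1.1.1 adds that symptoms after initial resolution of "oocysts in the stool and/or diarrheal symptoms, will be considered an AESI"; SAP 2.6.1.1 has closely similar text. Section 12.5.1 leaves the analysis of duration and time to resolution to the SAP.

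**SAP 2.5.3.** Duration variables are right-censored if rescue medication was taken. Kaplan-Meier times are censored if rescue comes before the event. After rescue, only stools below Grade 3 are set to missing.

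**The concern.** The words about clinical illness in the duration and resolution formulas select the participants, not the stools. Once someone meets the illness criterion, every Grade 3-5 stool counts, however isolated. Clear days between the illness and a stray stool then become part of the illness.

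Each later loose stool also moves resolution. Within the analysis, diarrhea can therefore never follow resolution. The safety text in both documents assumes that it can. The same participant could appear in the safety tables as a recurrence after resolution and in the efficacy tables as one long unresolved episode.

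Time to onset and time to resolution of diarrheal illness are named secondary endpoints, and Protocol 12.5.1 adds duration. They describe a challenge model that Protocol 1.2 intends for later studies of therapies and vaccines.

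**Working it through.** **1. The plan's own figure.** Take dosing as Day 1. A last loose stool on study day D gives (D − 1) + 3 = D + 2, the end of the second clear day. D = 8 gives 10 and D = 18 gives 20. The +3 therefore reproduces and contains the two-day window. The open question is which two-day run counts.

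**2. Internal consistency.** Onset starts at the first day of clinical illness, but duration starts at the first loose stool of any kind. The resolution definition equates the last day of clinical illness with the last diarrhea date. Each pair differs as soon as an isolated stool falls outside the illness.

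**3. One participant (assumed profile).** There are two Grade 3-5 stools on each of Days 6, 7 and 8, the first on Day 6 at 08:00 and the last on Day 8 at 20:00. Duration is 2 × 24 + 12 = 60 h. Add one isolated Grade 3 stool at 08:00, with no rescue yet given. Compare the SAP with an episode rule that starts at the first qualifying day and ends before the first two or more diarrhea-free days after two qualifying days.

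| Isolated stool | SAP duration | SAP days to resolution | Episode rule |
|---|---|---|---|
| none | 60 h | 10 | 60 h, day 10 |
| Day 2 | 6 × 24 + 12 = 156 h | 10 | 60 h, day 10 |
| Day 11 | 5 × 24 = 120 h | 13 | 60 h, day 10 |
| Day 14 | 8 × 24 = 192 h | 16 | 60 h, day 10 |
| Day 18 | 12 × 24 = 288 h | 20 | 60 h, day 10 |
| Day 20 | 14 × 24 = 336 h | 22 | 60 h, day 10 |

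**4. Group mean, ignoring censoring.** Assume 20 ill participants; Protocol 12.8.2 takes 70% with symptoms, and 30 × 0.70 = 21. One Day 18 case adds (288 − 60)/20 = 11.4 h to mean duration and (20 − 10)/20 = 0.5 day to mean time to resolution.

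For a range, let 5% to 21% of ill participants have one late stool between Day 11 and Day 18. The 21% is the outbreak relapse rate cited in Protocol 4.1; it is not a rate of isolated stools and serves only as an upper illustration.

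- Duration, low end: 0.95 × 60 + 0.05 × 120 = 63.0 h.
- Duration, high end: 0.79 × 60 + 0.21 × 288 = 107.9 h.
- Resolution, low end: 0.95 × 10 + 0.05 × 13 = 10.15 days.
- Resolution, high end: 0.79 × 10 + 0.21 × 20 = 12.1 days.

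Medians move less. With 19 of 20 participants at 60 h, the median stays at 60 h.

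**5. Censoring.** Infected participants are due nitazoxanide on Day 21 or once the Day 17 result is available. A stool on Day 20 puts SAP resolution at day 22, after a Day 21 rescue. A participant clear since Day 8 is then censored instead of resolved at day 10, which shifts the Kaplan-Meier curve later.

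**The case against.** A reader might infer that the SAP contradicts the protocol's resolution rule, and that the entry of none under "Change to protocol specified analyses" (SAP Section 4) is therefore wrong. The documents do not support that. The SAP restates the two-day rule and builds it into the +3. The protocol never says that the first two-day run is the one that counts, gives no formula, and defers the details to the SAP. What stands is a mismatch with the relapse language, not a breach of an explicit rule.

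A reader might also assume that any loose stool up to Day 28 counts in full. SAP 2.5.3 censors at rescue, so the uncensored illustration applies only before rescue. Even the Day 18 case assumes that treatment has not already followed the Day 17 result. Censoring does not remove the problem, as the Day 20 case shows. SAP 2.5.3 is also not fully clear, because loose stools after rescue are kept and its wording could be read to censor episodes already over.

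Nor do the documents show that the results cannot be compared with the durations in Protocol Table 4-1, since the table does not say how duration was defined.

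Several mitigations are real:

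- Number of days of illness rises by only one per isolated stool.
- Recurrence is tabulated among the events of special interest.
- Participants positive for other enteric pathogens leave the PD analysis set.
- Kaplan-Meier medians are robust to one case.

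The contrast with infection is only partial: infection duration is also last minus first, and recrudescence also runs to the last positive test.

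Anchoring on the last stool has one merit. Qualifying days need not be consecutive. With qualifying days on Days 6 and 10, a naive first-clear-run rule would end the episode before the illness definition was met. The replacement must guard against this.

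**Conclusion.** The point holds as a gap in the SAP's definitions. Duration and resolution have no episode boundary, and the onset, duration and resolution variables do not describe the same episode. Before rescue, one isolated stool can turn 60 h into 120 to 288 h (Days 11 to 18) or 156 h (Day 2), and can move resolution from day 10 to between day 13 and day 20. One Day 18 case among 20 ill adds 11.4 h to the mean; medians move much less. A stool on Day 20 or later can replace a day-10 resolution with a censored time.

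These sizes rest on the assumed stool profile, the assumed share of ill participants with such a stool, and rescue on Day 21. The documents give no frequency for isolated loose stools. The endpoints are descriptive and the primary analysis is unaffected, but the definitions should be corrected.

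**What to change.** In SAP 2.1.1.1:

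- Start duration at the first loose stool of the first qualifying illness day, matching the onset variable.
- End it at the last loose stool before the first run of at least two consecutive diarrhea-free days that occurs after the illness criterion (two qualifying days) has been met.
- Derive time to resolution from that same end point, still counted from dosing.
- Tabulate later loose stools as recurrence, with count and date.
- Keep the first-to-last span and last-stool resolution as a sensitivity analysis.

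State in SAP 2.5.3 that an episode which ended before rescue is counted as resolved and not censored.

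The cost is SAP wording and derivation code; no new data are needed. The downside is that later relapses leave the main duration and must be read from the recurrence table. Clear days between two separated qualifying days would still count.

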3.2 ABO809 administration and inpatient monitoring period

ABO809 will be administered at the study site on Day 1. All participants, whether or not they are symptomatic, will be domiciled in a unit with adequate infection control until completion of Day 10 assessments. Participants who experience symptoms will remain domiciled for the duration of the diarrheal illness up to a maximum of Day 21. After Day 10, participants will be released from the study site only after they have had no diarrheal stools for at least 24 hours. Signs, symptoms, stool characteristics and parasitological assessment of oocyst shedding will be monitored daily. Safety assessments will include physical exams, ECGs, vital signs, standard clinical laboratory evaluations (hematology, blood chemistry, and urinalysis), adverse event and serious adverse event monitoring (see Table 8-1).

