3.3 Follow-up period and End of Study

Participants will return for outpatient follow-up visits on Day 14, 17, 21, 24, and 28 for clinical assessments and to provide collected stool samples for analysis. To minimize the risk of long term asymptomatic shedding and recurrence, participants may receive nitazoxanide per the U.S. Prescribing Information (see Section 6.2.3).

If a participant experiences diarrhea after Day 10 (after the participant has been discharged from the study site), the participant may be readmitted, at the discretion of the Investigator, to remain domiciled until the cessation of symptoms or Day 21, whichever is earlier. If diarrhea is not associated with any additional risks to participants, the Investigator can decide that the participant can be managed in an outpatient setting. In this case, the participant is requested to make a reasonable effort to collect all diarrheal stool samples for delivery to the study site. If a participant is still experiencing diarrheal illness at Day 28, the participant's stool will be analyzed for ongoing shedding of oocysts and the participant may be referred to specialty care for further diagnostic work-up and treatment at the discretion of the Investigator.

All participants will return for a follow-up visit on Day 28 to provide collected stool samples. A physical examination and laboratory tests will also be conducted.

Commercially Confidential Information

Alternatively, between

Day 28 and Day 56, participants may seek medical support from his/her healthcare provider (HCP). Participants may come back to the study site for an unscheduled visit until EOS. The end of study (EOS) visit will occur on Day 56 via phone call. Additional Post-Study Follow-Up phone calls will be conducted after EOS at 6 and 12 months after ABO809 administration. During the phone calls, data will be collected on the development of new onset persistent symptoms that may be related to administration with ABO809, including but not limited to diarrhea, abdominal pain, eye pain and joint pain in all participants (see Section 10.1.1.1).

4 Rationale

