	Commercially Confidential Informat	tion	
Occult Blood			
Cryptosporidium Antigen by EIA ^{10, 12}			

Period	Post-Study Follow-Up		
Visit Name	Post-Study Follow-Up Call		
Days	6 Month Phone Contact Commercially Confidential Information	12 Month Phone Contact on	
lgA			
	Commercially Confidential Informa	tion	
Evaluation of Clinical Signs and Symptoms ⁶			
CHIM Diary			
Standard of Care Drug Administration (Nitazoxanide) ⁸			
Concomitant medications			
Adverse Events	S ¹⁵	S ¹⁵	
•	Commercially Confidential Information	on	
Safety Follow-Up Call for Study Participants	S	s	
Study completion information			

Commercially Confidential Information

² Serum pregnancy tests at Screening and Day 28. Urine pregnancy test at Baseline.

³ Before ABO809 administration.

⁴ Participants should make every attempt to bring self-collected stool specimen to the clinic for each Outpatient Follow-Up visit. In the 24 hours prior to each Outpatient Follow-Up visit, all stools should be collected.

⁵ During screening, the first diarrheal stool, and the first diarrheal stool with relapse after clinical clearance will be tested for enteral pathogenic micro-organisms.

⁶ Includes number and frequency of diarrheal episodes, stool weight, volume, and grading (see Section 8.3.2, Section 8.4.1, and Appendix 1). Additionally, includes evaluation of nausea, vomiting, abdominal pain or discomfort, abdominal tenderness, abdominal rebound, abdominal distension, fecal urgency, diarrhea, flatulence, tenesmus, poor appetite, dehydration, fever, and electrolyte imbalance

⁸ Nitazoxanide to be administered per Prescribing Information (i.e. 500 mg every 12 hours for 3 days). Nitazoxanide administration will be captured on the standard concomitant medication page, and no specific CRF is required.

Page **50** of **81** Protocol No. CABO809A02101

Period	Post-Study Follow-Up	
Visit Name	Post-Study Follow-Up Call	
Days	6 Month Phone Contact	12 Month Phone Contact

¹¹ Additional tests can be done at the discretion of the Investigator e.g., in the case of dehydration.

Commercially Confidential Information

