8.3 Efficacy

8.3.1 Cryptosporidium Antigen by EIA

To assess the incidence of *Cryptosporidium* infection, fresh stool samples will be collected at Screening and during the study as detailed in the Assessment Schedule (see Table 8-1). While participants are domiciled, all stools will be collected for grading and quantity record, however, up to 3 stool samples per day, each separated by approximately 4 hour intervals, will be analyzed by EIA CCI at a CLIA laboratory for parasitological assessment of oocyst shedding. If the participant passes less than 3 stools on any given day during domiciling (1 or 2) then these stool samples will be used for parasitological assessment.

Commercially Confidential Information

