Outpatient follow-up period: After the domicile period, participants will be followed on an outpatient basis ending on Day 56 following ABO809 administration. Participants will return for follow-up visits on Days 14, 17, 21, 24 and 28 for clinical assessments and to provide collected stool samples for analysis.

Safety Follow-Up Calls: Participants will be contacted by telephone on Days 35, 42, 49 and 56 to collect information on any adverse events that are considered related to administration with ABO809. Any participants who experience diarrheal symptoms between Day 28 and Day 56 may provide a stool sample for analysis and may return to the study site for an unscheduled visit to consult with the Investigator. Additional Post-Study Follow-Up phone calls will be conducted after EOS at 6 and 12 months after ABO809 administration.

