Cryptosporidium infection: is defined as the presence of oocysts in at least 1 stool sample starting 72 hours following the administration of ABO809 (or sooner if associated with symptoms suggestive of diarrheal illness), up to Day 10 or Day 28 (separately). If clinical symptoms associated with cryptosporidiosis occur earlier than 72 hours post-administration, then stool samples after the onset of symptoms can be collected for parasitological evaluation. Oocysts will be detected by a commercially available diagnostic EIA test and confirmed by a DFA test if the EIA is positive. The tests will be performed at a Clinical Laboratory Improvement Amendments (CLIA) certified laboratory. Samples that test negative for Cryptosporidium by EIA will be reported as negative for Cryptosporidium without confirmation by DFA.

Resolution of *Cryptosporidium* **infection:** A *Cryptosporidium* infection will be considered resolved when no evidence of *Cryptosporidium* is detected in stool samples collected over ≥ 2 consecutive days. Please refer to the definition of "Number of days to resolution of Cryptosporidium infection" for further details.

Number of days to Cryptosporidium infection onset: is defined as the first occurrence of positive EIA test if it is at/after 72 hours post-challenge, otherwise as the first occurrence of positive EIA test with clinical diarrhea symptoms (if earlier than 72 hours), minus the date of dosing.

Number of days of Cryptosporidium infection: is defined as all days that have at least 1 positive EIA test.

Number of days to resolution of Cryptosporidium infection: is defined as:

- 48 hours after the last occurrence of positive EIA test during the inpatient period following the initial admission into the unit or,
- 48 hours after the last occurrence of positive EIA test during the inpatient period following the readmission into the unit or during the outpatient period up to Day 20 (without clinical diarrhea symptoms and before the start of NTZ) or,
- if there is a clinical relapse during the outpatient period, 48 hours after the last occurrence of positive EIA test with GP60 result showing recrudescence or,
- if clinical relapse during the outpatient period with GP60 result showing reinfection, 48 hours after the last occurrence of positive EIA test before onset of clinical symptoms,

i.e., the last positive EIA test date minus the dosing date +3.

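### Number of days of Cryptosporidium infection counts positive-test dates, but after Day 10 the number of dates tested depends on whether the participant is domiciled, so the count reflects management as well as shedding

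*SAP*

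**What the plan says.** SAP 2.1.1.1 states that the number of days of Cryptosporidium infection "is defined as all days that have at least 1 positive EIA test". It gives no denominator and no rule for dates without a test, and SAP 2.5.4 rules out imputation.

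Sampling comes in two intensities:

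- **While domiciled.** Protocol Section 3: "Participants will be monitored daily for infection (parasitological evaluation) and diarrheal illness (clinical evaluation) during the domicile period". Protocol 8.3.1: "up to 3 stool samples per day, each separated by approximately 4 hour intervals, will be analyzed by EIA". This covers everyone to Day 10.
- **After discharge.** SAP 2.1.1: "Participants will return for follow-up visits on Days 14, 17, 21, 24 and 28". Protocol Table 8-1, footnote 4: "In the 24 hours prior to each Outpatient Follow-Up visit, all stools should be collected". If diarrhea after Day 10 is managed at home, Protocol 3.3 adds that "the participant is requested to make a reasonable effort to collect all diarrheal stool samples for delivery to the study site".

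Diarrhea decides who is domiciled after Day 10. Protocol 3.2: "Participants who experience symptoms will remain domiciled for the duration of the diarrheal illness up to a maximum of Day 21". For diarrhea that appears after discharge, Protocol 3.3 says that "the participant may be readmitted, at the discretion of the Investigator", again to Day 21 at the latest.

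SAP 2.5.3 right-censors the variables named as numbers of days when rescue medication is taken, with medians from Proc Lifetest and means from Proc Lifereg. On rescue at Day 10 the documents differ. Protocol 6.2.3 and SAP 2.3.4 make nitazoxanide mandatory from Day 10 when diarrhea has persisted until then; Protocol 4.5 makes it optional.

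**The concern.** A count of positive dates measures shedding only if participants have the same dates on which to be positive. After Day 10 they do not, and the difference is driven by symptoms. Two participants with identical shedding can receive different counts because one stayed in the unit. The dose may be changed between cohorts partly to alter the illness rate, so the share of participants kept in can also differ between dose groups. A difference in days of infection between doses, or between symptomatic and asymptomatic participants, could then come from the sampling schedule. Participants still shedding after discharge would also have their shedding understated.

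**Working it through.** The documents give no planned figure for this variable, so there is nothing to reproduce. The check is a direct count.

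**Inputs from the documents.** Daily sampling to Day 10 for all; daily sampling to Day 21 at most if domiciled; visits on Days 14, 17, 21, 24 and 28 otherwise, each with a 24-hour collection.

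**Assumptions.** One unbroken shedding course from day *a* to day *b*, positive on every sampled date, and no rescue before *b*. A 24-hour collection is credited either to the visit date alone or to two calendar dates (visit date and the day before).

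**Formulas.**
- Kept in to Day 21, *b* ≤ 21: *b* − *a* + 1.
- Discharged on Day 10, *b* ≥ 10: (10 − *a* + 1) + number of visit dates not later than *b*. The two-date version also adds each day before a visit that is not later than *b*.

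**Sampling opportunity, Days 11-21.** Domiciled: 11 dates. Discharged: 3 visit dates (14, 17, 21), or at most 6 calendar dates.

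**Counts for shedding from Day 5.**

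| Shedding | Kept in | Discharged, visit date only | Discharged, two dates | Ratios |
|---|---|---|---|---|
| Days 5-10 | 6 | 6 | 6 | 1.00 / 1.00 |
| Days 5-14 | 10 | 6 + 1 = 7 | 6 + 2 = 8 | 1.43 / 1.25 |
| Days 5-17 | 13 | 6 + 2 = 8 | 6 + 4 = 10 | 1.62 / 1.30 |
| Days 5-20 | 16 | 6 + 2 = 8 | 6 + 5 = 11 | 2.00 / 1.45 |

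With the first positive day at 4, 5 or 7 and the last from Day 10 to Day 28, the ratio runs from 1.00 to 2.33 (the maximum is Days 7-20: 14 against 6, visit dates only). For shedding to Day 14 it runs from 1.22 to 1.60.

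**Shorter stays, shedding Days 5-20, against 8 if discharged on Day 10.** Kept in to Day 12: 10. To Day 14: 11. To Day 17: 13. Readmitted on Days 12-21: 15.

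**With rescue on Day 10.** A kept-in participant shedding from Day 5 contributes Days 5-9 or 5-10, that is 5 or 6 days, censored. The discharged participant with shedding to Day 20 still contributes 8. The observed counts are now in the opposite order.

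**Candidate remedies.**
- Count from 72 hours (Day 4) to Day 10, shedding throughout: 7 against 7.
- Count only on common dates (to Day 10, then 14, 17, 21, 24, 28), shedding Days 5-20 without rescue: 8 against 8.
- Positive days over tested days for Days 11-28, shedding to Day 20: domiciled tested dates are 11-21, 24 and 28, giving 10/13 = 77%; discharged 2/5 = 40%. The ratio is 1.92, so the bias stays.
- First-to-last Duration, shedding Days 5-20: 20 − 5 = 15 days against 17 − 5 = 12 (15 against 15 with two-date collections). This is less affected, but not free of the schedule.

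**The case against.** The strongest reply is that SAP 2.5.3 already governs this variable. It is right-censored at rescue, and under the mandatory wording the participants kept in with diarrhea at Day 10 start nitazoxanide that day. They would not accumulate daily positives to Day 21. This stands, and it rules out an inference that a reader might draw: that the count is always, and greatly, inflated in symptomatic participants. The full inflation needs domicile without rescue, or readmission for diarrhea starting after Day 10, which the Day 10 rule does not clearly cover. Censoring does not cure the problem, however. It can turn the difference round, and the SAP does not say how a count that grows daily in some participants and every few days in others is to be censored.

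The size is also limited in most cases. Protocol 4.1 cites excretion confined to the first 14 days in up to 86% of participants with diarrhea. Domicile to Day 21 is a maximum, since release after Day 10 needs only 24 hours without diarrheal stools. Infected participants are due nitazoxanide on Day 21 or once the Day 17 result is available, so the Day 20 row is near the upper end.

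Outpatient sampling may be denser than five visits because of the request for diarrheal stools, and two footnotes to the EIA and stool-collection rows of Table 8-1 cannot be read. The five-visit schedule is therefore a working assumption for participants without diarrhea.

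Finally, the variable is not listed in SAP Table 1-1, and no test or symptomatic-versus-asymptomatic comparison is visible. That lowers the stakes. The variable is still defined, and SAP 2.5.3 gives it a method of analysis.

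**Conclusion.** The point holds for shedding that continues past Day 10. Without rescue, identical shedding can score up to about twice as high in a domiciled participant: about 1.2 to 1.6 times for shedding to Day 14, and 1.45 to 2.00 times for Days 5-20. There is no gap when shedding ends by Day 10. With nitazoxanide and censoring on Day 10, the observed count can reverse, 5-6 censored days against 8. The documents do not support a fixed direction; they support the statement that the count depends on management as well as on shedding.

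These sizes rest on continuous shedding, a positive result on every sampled date, and the visible visit schedule. The primary endpoint is unaffected. The mandatory and optional statements on nitazoxanide at Day 10 (Protocol 6.2.3 and SAP 2.3.4 against Protocol 4.5) must be reconciled, because the direction of the bias turns on them.

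**What to change.** In SAP 2.1.1.1, define the number of days of infection over the window that is sampled daily in everyone, 72 hours to Day 10. If a later window is wanted, count only on the schedule common to all participants: to Day 10, then Days 14, 17, 21, 24 and 28. Apply the same 24-hour collection rule to domiciled participants, and leave extra diarrheal stools out of the count.

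State how the SAP 2.5.3 censoring applies to this count, including rescue on or before Day 10, and reconcile the nitazoxanide passages.

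Do not substitute positive days over tested days for Days 11-28: domiciled tests cluster in the earlier days, when positives are likelier, so the ratio keeps the bias. First-to-last Duration can be reported as planned, with a note that it too depends on the sampling schedule.

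The cost is SAP wording and a derivation from stool records already collected. The downside is that the Day 10 count is capped at about 7 days and does not describe later shedding.
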